10.15 Laboratory Data Management

Samples will be tracked utilizing caTissue v1.2, an NCI caBIG-developed platform. caTissue has been installed at Duke, and has some pilot implementation projects underway. Data from this system will provide a near real-time accounting of all samples, shipping and results from contracted lab, and provide views of the data that may be integrated with views from the eCRF for reporting purposes. As with other data in the system, expectations for the presentation of sample information will be set by the patient milestone (initiation and follow-up visit activity), flagging inconsistencies and missing sample information at regular intervals.

10.16 Regulatory Compliance

Both systems are built and deployed in accordance with HIPAA and 21 CFR Part 11, with proper system testing and validation. Application development follows a strict Software Development Life Cycle (SDLC) model, ensuring accurate deployment of all data collection tools and systems.

11.0 STATISTICAL CONSIDERATIONS

The primary objective of this study to assess the activity of the study agent as measured by the proportion of patients who survive progression-free for at least 6 months after initiating study therapy in patients with bevacizumab-resistant persistent or recurrent epithelial ovarian, fallopian tube, or primary peritoneal carcinoma.

11.1 The study plan is a single arm, non-randomized, 2-stage phase II clinical trial.

11.2 Parameters employed to evaluate treatment efficacy and toxicity are:

11.2.1 Primary Endpoints:

11.2.1.1 The proportion of patients who survive progression-free for at least 6 months.

11.2.2 Secondary Endpoints:

11.2.2.1 The proportion of patients who have objective tumor response (complete or partial).

11.2.2.2 Frequency and severity of adverse effects as assessed by the active version of the NCI Common Toxicity Criteria.

11.2.2.3 Duration of progression-free survival and overall survival.

11.2.3 Translational Endpoints:

11.2.3.1 To measure baseline levels of VEGF and correlate with treatment outcome.

11.2.3.2 To measure baseline and on treatment levels of additional growth factors (listed in section 2.5) that may be co- or counter- regulated with VEGF and correlate with response to treatment.

11.2.3.3 To measure baseline and on treatment levels of coagulation and endothelial cell activation markers that may predict for thrombotic or bleeding risks related to treatment.

11.3 A total of up to 56 will be accrued at the rate of about 5 patients per month. If the 6-month progression-free survival rate is *observed to be* ≥ 0.20 the trial will be considered a success. Progression-free survival will be defined as the length of time from on-study to disease progression or death, whichever comes first. The study will use a 2-stage optimal design [15] to test the null hypothesis that the 6-month PFS rate is $\leq 13\%$ against the alternative hypothesis that this rate is $\geq 27\%$. The targeted accrual for the first stage will be 27 eligible and evaluable patients but permitted to range from 27 to 31 for PFS determination and administrative reasons. The critical value for the number of patients who survive progression-free for 6 months will be based on the first 27 patients who are both eligible and evaluable for 6 month PFS. An interim analysis will be done after accrual of these patients (Stage 1). After the accrual of these patients, further accrual will be

suspended until all patients have been followed for at least 6 months or until at least 4 patients (15%) are found progression-free at 6 months. If 3 or less of the patients are progression-free at 6 months, the therapy will be deemed ineffective. If 4 or more of the patients are progression-free at 6 months, another 29 patients will be accrued. If 10 or less of the 56 patients are progression-free at 6 months, the therapy will be deemed ineffective. If at least 11 patients (20%) are progression-free at 6 months, the therapy will be deemed effective and worthy of further research. These stopping rules are illustrated in the table below.

Stage	Sample Size	Minimum number of patients who must be progression-free at 6-months for therapy to be considered effective
1	27	4 (15%)
2	56	11 (20%)

This design has a one-sided Type I error of 0.10, a power of 0.90. The probabilities of early termination given the null and the alternative are 0.54 and 0.04, respectively. If exactly 11 responses are observed, the exact 80% confidence interval will be [0.13, 0.28]. If even one patient drops out or is lost-to-follow-up before progression, then we will not be able to tabulate the number of patients who are progression-free at 6 months. In this case, we will calculate the Kaplan-Meier curve and focus on the probability of surviving to 6 months as calculated by the Kaplan-Meier method. We will call this trial a success only if the lower 10% confidence bound of this probability is greater than 0.13.

Statistical Analysis of Secondary Aims

Secondary Aim 1 is to determine the proportion of patient who has an objective tumor response (complete or partial). To address this aim all responses will be tabulated: complete response, partial response, stable disease, progressive disease.

Secondary Aim 2 is to determine the frequency and severity of adverse events. To address this aim, all toxicities will be tabulated by type and grade.

Secondary Aim 3 is to estimate the distribution of PFS and overall survival (OS). PFS was defined above. OS is defined as the length of the interval from on-study to death due to any cause. Both PFS and OS will be estimated with the Kaplan-Meier curve. In addition, we will compare the PFS of patients who had prior bevacizumab resistance with that of patients who had prior bevacizumab and chemotherapy resistance. Specifically, within each of these two groups, we will describe PFS with a Kaplan-Meier curve and the 6-month PFS rate (with its 80% confidence interval). We expect the latter group to have worse PFS than the former.

Secondary Aim 4 is to elicit patient preferences for outcomes of ovarian cancer treatment. The distribution of rank preferences for each general attribute will be described using mean ranks as well as the proportions of times each concept was ranked as most

important, second most important, third most important, fourth most important, and least important. In the token ranking exercise, to describe the allocations of tokens across the general attributes, we will report means, standard deviations, and median numbers of tokens for each attribute. To examine consistency between token allocations with rank preferences, we will reverse order the rank preferences such that higher ranks correspond to higher preferences and compute correlation coefficients. We will test whether correlations between ranks and token counts differ between attributes using Spearman rank tests. We will also examine the proportion of patients who provided the highest token counts to their most preferred attribute and vice versa. In the ratings exercise, to describe respondents' ratings on the 5-point Likert scale representing level of concern with each attribute included in the DCE, we will report frequencies of ratings for each attribute as well as means to provide a summary measure.

Secondary Aim 5 is to characterize baseline quality of life and cancer-related symptoms. We will use descriptive characteristics to summarize baseline characteristics for the study cohort enrolled at Duke. These characteristics will include summary scores from the NFOSI-18 and the FACT-GOG-Ntx. We will report means, medians, and standard deviations for continuous variables and counts and proportions for categorical variables.

Statistical Analysis of Translation Research Objectives

The association of PFS with baseline values of VEGF (continuous) will be tested with the proportional hazards model; VEGF will also be dichotomized at a clinically meaningful cut point and a Kaplan-Meier plot of PFS according to VEGF level will be made. An analogous procedure will be used to examine the association of PFS with baseline values of the growth factors listed Section 2.5.

THIS SPACE LEFT INTENTIONALLY BLANK

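### Minor: the success threshold written as an observed rate of at least 0.20 is, read literally, not met at the design's own cut-off of 11 of 56 (0.196)

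*Combined protocol and SAP*

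**What the plan says.** Protocol section 11.3 states the criterion for the primary endpoint in more than one form.

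- **As a rate.** Just after the accrual target of up to 56, the section says what happens if the observed 6-month progression-free rate is at least "0.20 the trial will be considered a success". No count stands beside this figure.
- **As a count.** After the stage 1 rule (stop at 3 or fewer of 27, otherwise add 29 patients), the final rule is: "If 10 or less of the 56 patients are progression-free at 6 months, the therapy will be deemed ineffective". It continues: "If at least 11 patients (20%) are progression-free at 6 months, the therapy will be deemed effective and worthy of further research". The stopping-rule table repeats 11 of 56 with the same 20% label, and shows the stage 1 minimum as 4 of 27 with a 15% label.
- **As a confidence bound, in one circumstance.** If any patient drops out or is lost before progression, the count is given up for a Kaplan-Meier estimate: "We will call this trial a success only if the lower 10% confidence bound of this probability is greater than 0.13".

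The section states a one-sided type I error of 0.10, power of 0.90, early-termination probabilities of 0.54 and 0.04 under the null (13%) and the alternative (27%), and an exact 80% interval of 0.13 to 0.28 for a result of exactly 11.

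**The concern.** The rate sentence and the count rule do not describe the same cut-off. Eleven of 56 is just under 0.20, so a reader who compares the observed proportion with the printed threshold finds it not met at the very count that the design treats as the smallest success.

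The rate sentence comes first, stands alone, and refers expressly to the observed rate, so it cannot be taken as a remark about the true rate. Anyone who applied it unrounded would be using a stricter rule than the one that carries the stated error rates. The disagreement falls on the borderline result, where a pre-specified rule most needs to be unambiguous.

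**Working it through.** **Inputs, all from section 11.3.** Null rate 0.13; alternative rate 0.27; stage 1 of 27 patients, stopping at 3 or fewer; 29 more patients for a total of 56; final success at 11 or more; rate threshold 0.20.

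**1. The threshold as a count**

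- 0.20 × 56 = 11.2, so the smallest whole number of patients that meets the rate threshold is 12.
- 11/56 = 0.1964, below 0.20.
- 12/56 = 0.2143, above 0.20.
- For comparison, 4/27 = 0.148, printed as 15%. The section rounds to whole percents, which explains the 20% beside the 11.

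**2. The plan's own operating characteristics**

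Let X1 be the number progression-free among the first 27 and X2 the number among the next 29. For a final cut-off c and true rate p,

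P(success) = Σ over x1 from 4 to 27 of P(X1 = x1) × P(X2 ≥ c − x1),

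with X1 ~ Binomial(27, p) and X2 ~ Binomial(29, p). Early termination is P(X1 ≤ 3).

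| Quantity | Stated | Computed with c = 11 |
|---|---|---|
| Type I error (p = 0.13) | 0.10 | 0.0961 |
| Power (p = 0.27) | 0.90 | 0.9013 |
| Early termination, null | 0.54 | 0.527 |
| Early termination, alternative | 0.04 | 0.042 |
| Exact 80% interval at 11/56 | 0.13 to 0.28 | 0.129 to 0.281 |

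The error rate and power reproduce. Early termination under the null is about one point below the stated value; it depends only on stage 1 and has no bearing on this point.

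**3. The rate threshold taken literally, and the difference**

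| True rate | P(success), at least 11 | P(success), at least 12 | Difference = P(stage 1 passed, total exactly 11) |
|---|---|---|---|
| 0.13 | 0.0961 | 0.0511 | 0.0450 |
| 0.20 | 0.5500 | 0.4320 | 0.1180 |
| 0.27 | 0.9013 | 0.8493 | 0.0520 |

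The last column is the probability of the one outcome on which the two forms differ. Over all true rates its maximum is 0.1182, reached near p = 0.196.

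With the literal threshold the type I error falls to 0.051 and the power to 0.849, short of the stated 0.90. The stated pair therefore belongs to the count rule.

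**The case against.** The best reply is that this is a rounding convention which the section explains itself. It ties 20% to 11 of 56 twice, treats 4 of 27 in the same way, and prints its probabilities to two decimals; at that precision 11/56 is 0.20. The rate sentence also says what follows if the threshold is met, not only if it is met. It therefore does not call 11 of 56 a failure, and no count from 0 to 56 is formally classified in two ways. To go wrong, an analyst would have to read the sentence as a necessary condition, leave 0.20 unrounded and ignore the explicit count rule. Finally, the probabilities of ending on exactly 11 assume that the count is used at all, and one dropout before progression moves the decision to the Kaplan-Meier bound.

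Most of this stands, and it is why the point is minor. The intended rule is not in doubt, and the unconditional chance that the wording matters is no higher than the figures above. The quoted 80% interval does not settle the cut-off either, because it follows from 11 and 56 whatever the cut-off is; the evidence is the explicit count rule and the matching error rates.

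What does not stand is that nothing needs correcting. A rounded percentage in brackets beside a count is harmless because the count governs. Here the rounded figure stands alone as a decision threshold, and the rounding has carried it above the value it represents.

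**Conclusion.** The concern holds, as a minor error of statement. The rate sentence misstates the primary cut-off: 0.20 cannot be reached with 11 of 56, and the design's cut-off is 11.

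The consequence is confined to one result, exactly 11 of 56. An unrounded reading would cost about 5 points of power (0.901 to 0.849) and would lower the type I error (0.096 to 0.051), so it cannot produce a false claim of activity. The count rule, the sample size and the stated error rate and power are not at fault.

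These figures rest on the exact two-stage binomial model with 27 and 29 patients, adherence to the stage 1 stop, and 6-month status known for all 56.

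**What to change.** Delete the sentence that gives the 0.20 threshold, or replace it with a count: success if at least 11 of 56 patients are progression-free at 6 months, when all patients can be tabulated. Changing the 20% label on the 11 to 19.6% is optional.

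Leave the sample size, both boundaries, the type I error and the power as they are. The edit does not reduce the plan to a single success rule, because the Kaplan-Meier criterion still applies when a patient drops out or is lost before progression. The cost is one sentence, with no change to the design.

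### The 80% interval given for 11 of 56 matches a single-stage calculation, and unrounded it contains the 13% null at the count where the two-stage test rejects

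*Combined protocol and SAP*

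**What the plan says.** Section 11.3 of the combined protocol and SAP describes the design: "The study will use a 2-stage optimal design [15] to test the null hypothesis" that the 6-month PFS rate is at most 13%, against an alternative of at least 27%. The rules are:

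- Stage 1, 27 patients: "If 3 or less of the patients are progression-free at 6 months, the therapy will be deemed ineffective".
- Continuation: "If 4 or more of the patients are progression-free at 6 months, another 29 patients will be accrued", for a total of 56.
- Final decision: "If at least 11 patients (20%) are progression-free at 6 months, the therapy will be deemed effective and worthy of further research".

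The section states a one-sided type I error of 0.10 and power of 0.90. It then illustrates the result at the decision boundary: "If exactly 11 responses are observed, the exact 80% confidence interval will be [0.13, 0.28", with the bracket closing after the upper limit. It does not say how the interval was calculated or whether it allows for the stage 1 look, and it gives the limits to two decimals.

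A separate rule covers incomplete follow-up. If any patient drops out or is lost before progression, the count is replaced by a Kaplan-Meier estimate at 6 months, and: "We will call this trial a success only if the lower 10% confidence bound of this probability is greater than 0.13".

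**The concern.** A two-sided 80% interval is the natural partner of a one-sided test at 0.10. Its lower limit should exceed the null rate exactly when the test rejects. If the interval is calculated as though 56 patients had been enrolled in one block, it rests on a different sampling plan from the test, and the two can disagree. They are most likely to do so at the boundary count, which is the case the plan chose to illustrate.

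What is at stake is the coherence of the report. With 11 of 56, the trial would declare the therapy effective and, at full precision, publish an interval that still includes the rate it claims to have ruled out.

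**Working it through.** **Inputs (section 11.3).** n1 = 27; stop if 3 or fewer; n2 = 29; n = 56; effective if 11 or more; p0 = 0.13; p1 = 0.27; one-sided alpha 0.10; interval level 80%, so 10% in each tail.

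**Step 1: reproduce the printed interval.** The single-stage Clopper-Pearson limits for 11 of 56 are beta quantiles:

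- Lower: Beta(0.10; 11, 46) = 0.1290
- Upper: Beta(0.90; 12, 45) = 0.2814

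These round to the printed limits, 0.13 and 0.28. None of the other methods tried gives both:

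| Method | Lower | Upper |
|---|---|---|
| Clopper-Pearson, single stage | 0.1290 | 0.2814 |
| Wald | 0.128 | 0.264 |
| Wilson | 0.137 | 0.273 |
| Jeffreys | 0.137 | 0.272 |
| Mid-P | 0.136 | 0.273 |
| Exact, two stage | 0.1310 | 0.2857 |

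**Step 2: the two-stage test.** Let U(p, s) be the probability of passing stage 1 and reaching a total of at least s:

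U(p, s) = sum over a = 4 to 27 of P(Bin(27, p) = a) × P(Bin(29, p) ≥ s − a)

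- Type I error: U(0.13, 11) = 0.0961, within the stated 0.10. This is also the exact one-sided p-value at 11 of 56.
- Power: U(0.27, 11) = 0.9013, matching the stated 0.90.

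**Step 3: where test and interval part.** The single-stage tail is P(Bin(56, 0.13) ≥ 11) = 0.1043, which is above 0.10. That is why the single-stage lower limit falls below 0.13. The difference, 0.1043 − 0.0961 = 0.0082, is the probability of having 3 or fewer successes in the first 27 and still reaching 11 by patient 56. The design makes those paths impossible because accrual stops. The single-stage interval counts them.

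**Step 4: the interval that matches the test.** Put 10% in each tail of the two-stage distribution:

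- Lower limit: solve U(p, 11) = 0.10, giving p = 0.1310
- Upper limit: solve 1 − U(p, 12) = 0.10, giving p = 0.2857

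This orders outcomes by stage. Ordering by the observed proportion gives the same tails, because every early-stopping result is at most 3/27 = 0.111, below 11/56 = 0.196.

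**Step 5: compare.**

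- Lower: 0.1310 − 0.1290 = 0.0020. The limit moves from below 0.13 to above it.
- Upper: 0.2857 − 0.2814 = 0.0043. At two decimals it changes from 0.28 to 0.29.

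**Optional estimate.** The uniformly minimum variance unbiased estimate at 11 of 56 is the sum over a = 4 to 11 of C(26, a − 1) × C(29, 11 − a), divided by the sum over the same range of C(27, a) × C(29, 11 − a). It equals 0.208, against the simple proportion 11/56 = 0.196.

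**The case against.** The best defence is that the sentence illustrates precision and decides nothing. A standard exact method reproduces it. The decision rests on the count, and the count rule holds its error rates. The printed interval is closed and shows 0.13 as its endpoint, so the plan never claims to exclude 13%, and the two-stage lower limit also prints as 0.13. At the plan's precision only the upper limit changes. All of this stands, and it keeps the point small. It does not rescue the figure: the upper limit is wrong for the design even at two decimals, and the interval and the test rest on different sampling plans.

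Three stronger readings are tempting, and none is supported.

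- **The same 11 of 56 would fail the plan's lower-bound rule.** That rule applies only when a patient drops out or is lost before progression. A complete 11 of 56 is decided by the count. The rule also uses a Kaplan-Meier bound of unnamed method: at 11 of 56 a plain Greenwood bound is 0.128 and a log-log bound is 0.134, so even a hypothetical application has no single answer. Naming that method is a separate matter, which restating this interval would not settle.
- **The single-stage interval covers too little.** At true rates of 13% and 20%, both intervals cover more than their nominal 80%. Coverage gives little reason to prefer either; agreement with the test does.
- **The simple proportion must be replaced because it is biased.** The downward bias is an average that includes trials stopped at 27 patients. Among trials that reach stage 2, the simple proportion is biased upward. Adjustment is a choice of inferential frame, and the plan commits to none.

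**Conclusion.** The point holds, as a minor one. The interval described as exact is not the exact interval for this design. It matches the single-stage Clopper-Pearson interval, 0.1290 to 0.2814, whereas inverting the plan's own two-stage test gives 0.1310 to 0.2857. At the minimum count called effective, the single-stage interval contains 13%, although the test rejects with p = 0.096.

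The limits move by only 0.002 and 0.004. Sample size, stopping rule, error rates and decision are all unaffected.

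The conclusion rests on two assumptions. First, that the plan used the single-stage method is inferred from its limits, because no method is named. Second, the two-stage figures take exactly 27 and then 29 evaluable patients with complete 6-month status, as the decision table does. The section allows stage 1 accrual of up to 31 but bases the stage 1 critical value on the first 27.

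**What to change.** In section 11.3, replace the interval for 11 of 56 with [0.131, 0.286], and label it as the exact 80% interval obtained by inverting the two-stage test. State that the same method will be used for the reported interval whenever the count is complete. Give three decimals wherever a limit is compared with 0.13.

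The bias-adjusted estimate (0.208 at 11 of 56) may be reported beside the simple proportion (0.196) as an optional supplement.

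The cost is one restated interval, one sentence naming the method, and a few lines of analysis code. Trial conduct does not change.

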5.3 Criteria for removal from treatment

5.3.1 Inability to tolerate Nintedanib at the lowest doses because of toxicity.

5.3.2 Patients may choose to withdraw from the study at any time for any reason.

5.3.3 Patients with evidence of disease progression or significant side effects will be removed from study.

5.3.4 Patients who become pregnant will be removed from the study.

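### The primary success rules in section 11.3 do not fully agree near the cut-off: 0.20 against 11 of 56, a Kaplan-Meier trigger with no written 6-month limit, and a bound with no named method

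*Combined protocol and SAP*

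**What the plan says.** All three statements are in section 11.3 of the combined protocol and SAP.

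- **Observed rate.** The trial succeeds if the observed 6-month PFS rate is at least "0.20 the trial will be considered a success".
- **Count.** "If at least 11 patients (20%) are progression-free at 6 months, the therapy will be deemed effective and worthy of further research". Ten or fewer of 56 is declared ineffective. The table under the rule repeats 11 of 56 with 20% in brackets.
- **Kaplan-Meier fallback.** "If even one patient drops out or is lost-to-follow-up before progression, then we will not be able to tabulate the number of patients"; the number meant is the 6-month count. The Kaplan-Meier probability at 6 months then replaces the count: "We will call this trial a success only if the lower 10% confidence bound of this probability is greater than 0.13".

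The operating characteristics are given once: "This design has a one-sided Type I error of 0.10, a power of 0.90". The word exact is attached only to the 80% interval for 11 observed responses, printed as 0.13 to 0.28. The 80% interval planned for the subgroup 6-month PFS rates (Secondary Aim 3) also has no stated method.

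**The concern.** These sentences decide whether the drug is called worthy of further research, so they should give one answer for one data set. Near 11 of 56 they may not.

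- 11 of 56 meets the count rule but, at 0.196, falls short of 0.20 unless rounded.
- The condition for the fallback is a loss without progression, with no time attached. Taken word for word, a patient lost in month 9 would displace a 6-month count that is fully known.
- The fallback fixes the estimator, the level (lower 10%) and the threshold (0.13), but no variance formula, scale or exact method. Standard choices fall on both sides of 0.13 close to the cut-off.

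At stake is a borderline verdict settled by a software default or by a choice made after the data are seen. The plan gives no error rates for the fallback.

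**Working it through.** **Inputs.** From section 11.3: null rate 0.13, alternative 0.27; stage 1 has 27 patients and continues with 4 or more progression-free; final analysis has 56 patients and succeeds with 11 or more; lower 10% bound compared with 0.13, so z = 1.2816. The documents give no dropout rate; 2%, 5% and 10% by month 6 are assumptions.

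**Step 1: reproduce the design.** P(success | p) = Σ over x from 4 to 27 of b(x; 27, p) × P(Y ≥ 11 − x), with Y ~ Bin(29, p). This gives 0.0961 at 13% and 0.9013 at 27%, matching the printed 0.10 and 0.90. Early termination is 0.527 and 0.042 (printed 0.54 and 0.04; the small gap has no bearing here). The exact 80% interval at 11/56 is 0.1290 to 0.2814, which rounds to the printed one. The quoted error rates are therefore those of the count rule.

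**Step 2: a strict 0.20.** 0.20 × 56 = 11.2, so 12 patients are needed. The probability of reaching stage 2 and ending with exactly 11 is 0.0450 at 13% and 0.0520 at 27%.

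- Type I error: 0.0961 − 0.0450 = 0.0511.
- Power: 0.9013 − 0.0520 = 0.8493.

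**Step 3: the bound on complete data.** With no loss before month 6 the Kaplan-Meier estimate is S = k/56, and Greenwood gives se = √(S(1 − S)/56). For k = 11, S = 0.1964, se = 0.0531 and z × se = 0.0680.

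- Plain: 0.1964 − 0.0680 = 0.1284.
- Log: 0.1964 × exp(−0.0680/0.1964) = 0.1389.
- Log-log: ln S = −1.6275; exp(z × se/(S × 1.6275)) = exp(0.2128) = 1.2372; exp(−1.6275 × 1.2372) = 0.1335.
- Exact (Clopper-Pearson): 0.1290.

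| Progression-free | Plain | Exact | Log-log | Log |
|---|---|---|---|---|
| 10/56 | 0.1130 | 0.1141 | 0.1186 | 0.1237 |
| 11/56 | 0.1284 | 0.1290 | 0.1335 | 0.1389 |

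All four fail at 10/56, and at 12/56 all pass (0.144 to 0.154). Only 11/56 splits them. This is the case that arises if a loss after month 6 is allowed to trigger the fallback.

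**Step 4: losses before month 6.** Every ordering of losses among the patients not known to be progression-free was enumerated. Entries are orderings that pass.

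| Known progression-free | Losses | Orderings | Plain | Log-log | Log |
|---|---|---|---|---|---|
| 11 | 1 | 45 | 45 | 45 | 45 |
| 11 | 2 | 990 | 990 | 990 | 990 |
| 11 | 3 | 14,190 | 14,190 | 14,190 | 14,190 |
| 10 | 1 | 46 | 0 | 3 | 12 |
| 10 | 2 | 1,035 | 112 | 345 | 880 |
| 10 | 3 | 15,180 | 5,674 | 11,277 | 15,180 |

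These are counts of orderings, not probabilities. At a true rate of 27%, 10 known with one early loss occurs in 1.3%, 1.3% and 0.6% of trials at 2%, 5% and 10% dropout; 10 known with two losses in 0.5%, 1.2% and 1.2%.

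**Step 5: simulation.** Exponential PFS, independent exponential dropout, stage 1 on the first 27 evaluable of up to 31, final analysis on 56, Kaplan-Meier used only after a loss before month 6; two runs of 100,000 trials per scenario, averaged.

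| Dropout | Power at 27%: plain / log-log / log | Type I error at 13%: plain / log-log / log |
|---|---|---|
| 2% | 0.8885 / 0.8910 / 0.8964 | 0.0876 / 0.0899 / 0.0960 |
| 5% | 0.8736 / 0.8811 / 0.8931 | 0.0783 / 0.0852 / 0.0985 |
| 10% | 0.8518 / 0.8675 / 0.8844 | 0.0695 / 0.0816 / 0.0998 |

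The log minus plain gap in power is 0.8, 2.0 and 3.3 points. Separate simulations put disagreement among the three scales at about 1%, 2% and 3% of trials at 13% and at 27%, and about 2%, 5% and 7% at an intermediate true rate of 20%.

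**The case against.** The strongest reply is that the intended rule can be recovered from the text. Much of this stands.

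- **Trigger.** The sentence gives its own reason: the 6-month count can no longer be tabulated. That is untrue of a loss after month 6. A reader might infer that a late loss is meant to overturn a complete 11 of 56; the stated reason speaks against it. Even read that way, a late-only loss reverses a true 11/56 in 0.1% to 0.4% of simulated trials, and among the Greenwood scales only for the plain one. What stands is a missing limit in the wording.
- **0.20 against 11 of 56.** A reader might infer that the sponsor requires 12. The count rule is explicit, appears in text and table with 20% beside it, and is the one that yields the quoted error rates. This is rounding, though the two sentences still conflict if applied strictly.
- **Withdrawal.** Section 5.3 says "Patients may choose to withdraw from the study at any time for any reason", but under removal from treatment. Section 9.1 continues follow-up after study withdrawal, and section 8.1.3.5 asks for progression to be documented after treatment stops. Section 5.3 therefore does not show that losses will be common. Section 11.3 itself does foresee them.
- **Bound.** With 11 known progression-free and up to three early losses, every Greenwood scale passes, so on the intended trigger the method did not overturn such a trial in any ordering checked. It matters for trials with fewer known successes plus losses.
- **Choice of method.** Log-log is not uniquely right. Log also agrees with the count rule on complete data, stays at about 0.10 and has slightly more power.

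**Conclusion.** Minor, and it holds. The three statements agree only after rounding 0.196 to 0.20, reading a 6-month limit into the trigger, and supplying a bound method that the plan does not name. For early losses, the method changes the verdict only in borderline trials: about 1% to 3% of trials at a true rate of 13% or 27%, with assumed dropout of 2% to 10%. Power differs by about 1 to 3 points between plain and log.

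A reader might infer that the fallback inflates the false-positive rate. The simulations do not support that: type I error stays at or below about 0.10 on all three scales. Nor should power be quoted as 0.85 for complete data under a plain bound, because on the intended reading the count rule applies there.

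The sizes rest on assumed dropout, exponential times and dropout independent of prognosis. They also depend on how stage 1 treats losses: a separate simulation of 20,000 trials per case, with the stage 1 gate on the observed count in the first 27, gave log-log power of 0.877 and 0.851 at 5% and 10% dropout.

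**What to change.** In section 11.3:

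1. Replace the observed-rate criterion of 0.20 with at least 11 of 56.
2. Use the Kaplan-Meier rule only if a patient is lost before 6 months without progression or death; otherwise keep the count rule.
3. Name one bound that agrees with the count rule on complete data. A one-sided 90% Greenwood lower bound on the log-log scale is one suitable option, and the log scale is another. Plain and exact bounds do not agree at 11/56.
4. State that type I error 0.10 and power 0.90 belong to the count rule and that power is slightly lower under the fallback: about 0.87 to 0.89 for log-log at assumed dropout of 10% to 2%.

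The cost is a few sentences and no extra patients. The stated power becomes slightly less favourable. Because Kaplan-Meier gives partial credit to lost patients, some successes will have fewer than 11 known progression-free. Under log-log this is 0.3%, 1.5% and 5% of trials at 27%, and 0.3%, 1.2% and 2.9% at 13%, for 2%, 5% and 10% dropout. The plan should say that this is accepted.
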